APPENDIX 12. AESI – SEXUAL DYSFUNCTION

Anorgasmia
Disturbance in sexual arousal
Dyspareunia
Ejaculation delayed
Ejaculation disorder
Ejaculation dysfunction
Ejaculation failure
Erectile dysfunction
Female orgasmic disorder
Female sexual arousal disorder
Female sexual dysfunction
Inadequate lubrication
Libido decreased
Libido disorder
Loss of libido
Male orgasmic disorder
Male sexual arousal disorder
Male sexual dysfunction
Orgasm abnormal
Orgasmic sensation decreased
Sexual dysfunction
Vulvovaginal dryness

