13.4. Monitoring and Recording of Adverse Events

AE data collection will begin after a subject signs the ICF and will continue until completion of the final safety follow-up visit. Any AE or SAE having an onset after the final safety follow-up visit will not be collected or reported unless the investigator feels that the event may be related to the study drug.

Subjects will be instructed by the investigator or designee to report the occurrence of any AE. All volunteered, elicited, and observed AEs are to be recorded on the AE eCRFs.

The investigator will assess all AEs regarding any causal relationship to the study drug (see Section 13.3), the intensity (severity) of the event, action taken, and subject outcome.

The following criteria should be used to guide the assessment of intensity (severity):

- **Mild:** Causes awareness of sign or symptom, but is easily tolerated; does not interfere with usual activities
- **Moderate:** Causes discomfort enough to interfere with usual activities
- **Severe:** Is incapacitating; results in inability to work or perform usual activities

All AEs will be followed until resolution, until deemed stable by the investigator, or until the subject is deemed by the investigator to be lost to follow-up.

For clinical study safety reporting purposes, the most recent version of the IB will be used as the reference document to designate event expectedness.

Withdrawal from the study as a result of an AE and any therapeutic measures that are taken shall be at the discretion of the investigator. If a subject withdraws from the study for any reason, any ongoing AEs will be followed until resolution, until deemed stable by the investigator, or until the subject is deemed by the investigator to be lost to follow-up.

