In the last week, have you had pressure or tightness in your chest, or choking feelings? IF YES: How bad has that been? RESPIRATORY SYMPTOMS (pressure or constriction in chest, choking feelings, sighing, dyspnea):

What about sighing, or shortness of breath? IF YES: How bad has that been?

0 – not present
 1 – mild
 2 – moderate
 3 – severe
 4 – very severe

SIGH-A	MILD:	Occurs irregularly and for short periods of time.
	MODERATE:	Occurs more constantly and of longer duration, requiring considerable effort on the part of the subject to cope with it.
	SEVERE:	Continuous and dominates the subject's life.
	VERY SEVERE:	Incapacitating.

In the last week, have you had trouble swallowing? Have you had stomach pain or fullness, gas, nausea, vomiting, burning or rumbling in your stomach, loose bowels, or constipation. IF YES: How bad has that been? Have you lost weight in the past week? IF YES: How much? Have you been trying to lose weight? DO NOT RATE LOSS OF WEIGHT DUE TO DIETING.

GASTROINTESTINAL SYMPTOMS (difficulty in swallowing, wind, abdominal pain, burning sensations, abdominal fullness, nausea, borborygmi, looseness of bowels, loss of weight, constipation):

0 – not present
1 – mild
2 – moderate
3 – severe
4 – very severe

In the past week, have you had to urinate frequently? Have you had the urge to?

GENITOURINARY SYMPTOMS (frequency of micturition, urgency of micturition, amenorrhea, menorrhagia, development of frigidity, premature ejaculation, loss of libido, impotence):

How has your interest in sex been in the past week? (Here, I'm not asking about performance but about your interest in sex. How much did you think about it?).

0 – not present
1 – mild
2 – moderate
3 – severe
4 – very severe

FOR WOMEN: Have you had trouble having an orgasm in the past week? (When did that start?) Have you had your period in the last month or so? IF NOT: Do you know why not? IF YES: Was it especially heavy?

FOR MEN: Have you had trouble with premature ejaculation (coming too soon) in the past week? How about trouble keeping an erection? (When did that start?)

In the past week, has your mouth been dry? Have you had any flushing in your face, or have you been pale? Have you felt lightheaded, or had any tension headaches? How about feeling the hair rise on your arms, the back of your neck, or your head? Have you tended to sweat a lot in the past week? FOR EACH SX: How bad has that been?

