3.7.3. Adverse Events of Special Interest

Adverse events of special interest (AESIs) will be summarized by Preferred Term and by prior ALKS 5461 exposure and overall during treatment period for the Safety Population / Post-discontinuation Safety Population for any TEAEs or PDEAEs of special interest. The following summaries will be created for AESI:

- TEAEs associated with abuse potential
- TEAEs associated with dependence
- PDEAEs associated with withdrawal
- TEAEs associated with suicidal ideation and behavior
- TEAEs associated with hypomania / mania
- TEAEs associated with central nervous system (CNS) depression and sedation
- TEAEs associated with respiratory depression
- TEAEs associated with orthostasis / hypotension
- TEAEs associated with hypersensitivity

- TEAEs associated with slowing of ventricular repolarization
- TEAEs associated with hepatic effects
- TEAEs associated with sexual dysfunction

TEAEs associated with abuse potential will be presented by Adhoc System Organ Class and Preferred Term, where Adhoc System Organ Class is manually classified by Alkermes medical director as 3 categories: abuse behavior, euphoria related, and non-specific.

TEAEs associated with dependence will be presented for subjects with any exposure, ≥4 weeks exposure, and <4 weeks exposure, respectively.

PDEAEs associated with withdrawal will be presented for subjects with any exposure, ≥4 weeks exposure, and <4 weeks exposure, respectively. AESIs associated with withdrawal are PDEAEs that occur from >2 to 16 days post last dose as this is the period during which physiological opioid withdrawal presents by considering half-lives of both BUP and SAM.

Supportive AE listings will be provided for each special interest group. Narratives will be provided for clinically meaningful events within each AESI group.

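### The sexual-dysfunction AESI list names delayed and failed ejaculation but not premature ejaculation, so such an event would be missed if coded to its own preferred term

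*SAP*

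**What the plan says.** SAP Section 3.7.3 states that "Adverse events of special interest (AESIs) will be summarized by Preferred Term and by prior ALKS 5461 exposure" and overall. One of the planned summaries is "TEAEs associated with sexual dysfunction". Each AESI group also gets a supportive listing, and clinically meaningful events within a group get narratives.

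Appendix 12 supplies the preferred terms for this group. Four concern ejaculation: "Ejaculation delayed", "Ejaculation disorder", *Ejaculation dysfunction* and "Ejaculation failure". Broader terms are also listed, among them "Male sexual dysfunction", *Sexual dysfunction* and *Male orgasmic disorder*. Premature ejaculation is not listed.

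The HAM-A interview guide (Protocol Appendix I) names premature ejaculation in its genitourinary item. Its prompt begins "FOR MEN: Have you had trouble with premature ejaculation (coming too soon) in the past week". On safety reporting, Protocol Section 13.4 says: "All volunteered, elicited, and observed AEs are to be recorded on the AE eCRFs".

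**The concern.** The list does not rely on umbrella terms alone. It names two specific ejaculatory complaints as well as the general ones, and gives no reason for leaving out a third that the trial's own instrument treats as a sexual symptom. Section 3.7.3 offers no membership rule for this group beyond the appendix list. An event coded to an unlisted term would therefore not be counted, however clearly it is a sexual complaint.

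What is at stake is the completeness of one descriptive safety summary. A man whose only sexual TEAE is premature ejaculation might not count as a subject with a sexual-dysfunction AESI, and the reported proportion would then be low.

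**Working it through.** The plan gives no figure to reproduce here. The check is a count and a comparison of sections, followed by an illustration on assumed inputs.

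**1. Count of Appendix 12.** There are 22 terms. Four concern ejaculation (delayed, disorder, dysfunction, failure) and none names premature ejaculation. Adding it would make 23.

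**2. HAM-A item against the list.**

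| Sexual complaint in the HAM-A genitourinary item or its prompts | Counterpart in Appendix 12 |
|---|---|
| Loss of libido | *Loss of libido* (same words) |
| Impotence; trouble keeping an erection | *Erectile dysfunction* (by meaning) |
| Trouble having an orgasm (women's prompt) | *Anorgasmia*, *Female orgasmic disorder* (by meaning) |
| Frigidity | No term in the same words; the female arousal and libido terms are the nearest |
| Premature ejaculation | No specific term; only the general ejaculation and sexual-dysfunction terms |

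Among the complaints in the item that apply to men, premature ejaculation is the only one without a specific counterpart.

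**3. Can the complaint surface during treatment?** Protocol Table 2 schedules the HAM-A at baseline and Weeks 4, 8, 14, 26, 38 and 52, which is 7 visits. The baseline assessment describes the week before dosing in this study, or is carried over from the antecedent study, so 7 − 1 = 6 scheduled visits could bring out a treatment-emergent complaint. Section 13.4 then provides a route onto the AE form if the investigator judges the complaint to be an AE.

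**4. What happens after coding?** SAP Section 3.7.2 codes AEs with MedDRA 19.0. There are two cases:

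- Coded to a listed term (for example the general ejaculation-disorder term): the event is in the AESI table and nothing is lost.
- Coded to a separate premature-ejaculation term: the event is outside the AESI table, its listing and the narrative pool. It remains in the TEAE tables by system organ class and preferred term and in the by-subject AE listing.

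The dictionary is not in the documents, so they do not settle which case applies.

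**5. Illustration of size (assumed inputs).** Only the planned enrolment of about 1,500 comes from the documents. Assume that all are dosed, that 30% to 40% are men, and that 0.5% to 2% of men have such a TEAE coded to its own term and no other listed sexual event.

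- Men: 1,500 × 0.30 = 450 to 1,500 × 0.40 = 600.
- Omitted: 450 × 0.005 = 2.25 to 600 × 0.02 = 12 men.
- As a share of all subjects: 2.25 / 1,500 = 0.15% to 12 / 1,500 = 0.8%.

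If coding goes to a listed term, the omission is 0. The full range under these assumptions is therefore 0 to 12 men, or 0 to 0.8 percentage points on the overall rate.

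**The case against.** The strongest objection is that the effect depends on a dictionary the documents do not contain. Appendix 12 includes general terms that could take in this complaint, and the match between impotence and *Erectile dysfunction* is itself an inference. Demanding an exact term for one complaint while accepting an inferred match for another would be uneven. This stands to the extent that the omission must be stated as conditional. It does not explain why the list names two specific ejaculatory complaints and not the third.

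Several stronger readings are tempting, and the documents do not support them:

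- **Every man is asked about this symptom.** The interview guide requires only the first question of each item to be asked exactly as written, and in this item that question is about urination. The prompt for men comes later, and follow-up questions are used as needed.
- **The study therefore records it.** The HAM-A is an efficacy scale, and no rule turns an answer on it into an AE. Under Protocol Section 13.1, a complaint present before consent goes to medical history unless it worsens. The HAM-A shows that the symptom is foreseeable, not that it is routinely captured as a TEAE.
- **Such events never reach the sexual-dysfunction result.** That is so only if they are coded outside every listed term.
- **Only one direction of ejaculatory change can be seen.** The general ejaculation terms carry no direction.
- **The event vanishes from the report.** It stays in the general TEAE tables and AE listings. There, however, it is one row among many, and an uncommon event would not reach the tables restricted to terms in at least 5% of subjects. HAM-A item scores are listed but not summarized, so they do not fill the gap.

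It is also fair to say that the list is a sponsor's medical choice in a study without a reference arm or hypothesis test, and that no stated rule is broken.

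**Conclusion.** The point holds in a conditional and minor form. The gap in Appendix 12 is a matter of fact. Its consequence rests on two things the documents do not show: that MedDRA 19.0 gives the complaint its own preferred term, and that at least one man without another listed sexual event reports it as a TEAE. If either fails, nothing is lost. If both hold, the sexual-dysfunction AESI count is low by those men. The illustrative range of 0 to 12 men indicates scale only and is not an estimate. No conclusion of the trial is shown to change.

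**What to change.** Add 'Premature ejaculation' to Appendix 12. Before database lock, check the coded AE dataset once for any other sexual-function preferred terms not on the list, and add any found with a dated note in the SAP. If the sponsor prefers to leave the term out, the SAP should say why.

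The cost is one appendix line, one pass through the coded terms, and a rerun of one AESI table and its listing. The reported rate may rise slightly. If coding already goes to a listed term, the addition changes nothing and does no harm.
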